7.2.1.1. Adverse Events of Special Interest

An AESI (serious or non-serious, related or not related) is an event of scientific and medical concern specific to the sponsor’s product or program.

Efgartigimod treatment induces reductions in IgG levels, and there is a potential risk for infections associated with the low IgG levels. As such, any infection will be considered AESI in this trial. Further characterizing information will be collected in the eCRF, such as: location of infection, relationship to underlying condition, medical history and concomitant medication, reoccurrence of previous infection, previous rescue therapy, any confirmatory procedure, culture or urgent medical intervention.

7.2.1.2. Reporting of Adverse Events and Serious Adverse Events

All AEs that occur during the trial from signature of the ICF until the last study visit are to be recorded on the appropriate AE pages (either “serious” or “non-serious”) in the eCRF. The

investigator should complete all the details requested, including dates of onset, time of onset, stop date (when applicable), stop time (when applicable), severity, action taken, outcome, and relationship to efgartigimod, and to trial procedures. Each event should be recorded separately in the eCRF.

All AEs spontaneously reported by the patient or reported in response to the open question from the trial personnel: “*Have you had any health problems since the previous visit or since you were last asked?*,” or revealed by observation will be collected and recorded in the eCRF. When collecting AEs, the recording of diagnoses is preferred (when possible) to recording a list of signs and symptoms. However, if a diagnosis is known and there are other signs or symptoms that are not generally part of the diagnosis, the diagnosis and each sign or symptom will be recorded separately.

Any SAE, including death due to any cause, which occurs during this trial after signature of the ICF, whether or not related to efgartigimod, must be reported immediately (within 24 hours of the trial site’s knowledge of the event). All SAEs will be recorded (within 24 hours) on the paper SAE Report Form and the AE form in the eCRF, the investigator or delegated site staff should check that all entered data are consistent. An alert email for the SAE report in the eCRF will then automatically be sent by email to the sponsor’s designated CRO safety mailbox via the electronic data capture (EDC) system. The paper SAE Report Form should be faxed or emailed to the sponsor’s designated CRO (see the [Safety Mailbox/Fax](#) details on the title page of this protocol).

The report will contain as much available information concerning the SAE to enable the sponsor (or an authorized representative) to file a report, which satisfies regulatory reporting requirements. These timelines apply to initial reports of SAEs and to all follow-up reports.

Criteria for documenting the relationship to efgartigimod, as well as severity, outcome, and action taken will be the same as those previously described.

The investigator shall report within 24 hours any SAE (s)he becomes aware of after a patient’s last visit if a causal relationship with the investigational product is suspected. Such a serious adverse reaction (SAR) is to be collected and reported as previously described for SAEs.

All SAEs that are spontaneously reported within 30 days after the last trial visit are to be collected and reported as previously described and all efforts should be made to follow-up until resolution.

Additional follow-up information should be completed and entered on a paper SAE Report Form and sent by fax/email to the sponsor’s designated CRO.

7.2.1.3. Reporting of Serious Adverse Events to Regulatory Authorities and Investigators

The sponsor’s designee will be responsible for reporting all SUSARs, the Analysis of Similar Events (AOSE), and any other applicable reports to regulatory authorities, ethics committees, and investigators, in accordance with national regulations in the countries where the trial is conducted. Relative to the first awareness of the event by/or further provision to the sponsor’s designee, SUSARs will be submitted within 7 days for fatal and life-threatening events and 15 days for other SUSARs, unless otherwise required by national regulations. The sponsor’s designee will also prepare an expedited report for other safety issues where applicable.

The investigational site will also forward a copy of all expedited reports to his or her IEC/IRB in accordance with national regulations.

7.2.1.4. Follow-up of Adverse Events and Serious Adverse Events

Any AEs observed from signing the ICF to the last study visit will be followed up to resolution, until the patient is lost to follow-up, or until the patient withdraws consent. Resolution means that the patient has returned to a baseline state of health or the investigator does not expect any further improvement or worsening of the AE.

Every effort should be made to follow all (S)AEs considered to be related to efgartigimod or trial procedures until an outcome can be reported. If the patient is lost to follow-up, all AEs will be categorized based on the investigator's last assessment.

All SAEs that are spontaneously reported after the last study visit are to be collected and reported as previously described (as per Section 7.2.1.2) and will be followed up. During the trial period, resolution of SAEs (with dates) should be documented on the SAE page of the eCRF and in the patient's medical record to facilitate source data verification. If, after follow-up, return to the baseline status or stabilization cannot be established, an explanation should be recorded on the SAE page of the eCRF.

All pregnancies reported during the trial should be followed until pregnancy outcome.

For SAEs, non-serious AEs, and pregnancies, the sponsor's designee may follow-up by telephone, fax, electronic mail, and/or a monitoring visit to obtain additional case details and outcome information (eg, from hospital discharge summaries, consultant reports, or autopsy reports) in order to perform an independent medical assessment of the reported case.

7.2.1.5. Reporting and Follow-up Requirements for Pregnancies

7.2.1.5.1. Pregnancies in Female Patients

Urine pregnancy tests will be conducted and analyzed locally at visits as detailed in the General Schedule of Assessments for Part A (Table 1) and for Part B (Table 2). Results will be recorded in the eCRF.

If a patient becomes pregnant after the administration of efgartigimod and up to 90 days after the patient received the last infusion, the sponsor and/or sponsor's designee should be informed immediately (ie, within 24 hours of the trial site's knowledge of the event). The following actions will be performed:

- The patient should immediately be discontinued from trial treatment.
- The patient should have the planned ED assessments.
- All planned assessments (see Sections 4.4 and 5.4) must be performed unless contraindicated by pregnancy (harmful to fetus) or unless the patient withdraws informed consent.

The investigator must update the patient with information currently known about potential risks and about available treatment alternatives. The pregnancy should be followed up to determine outcome, including spontaneous or voluntary termination, details of the birth, and the presence or

absence of any birth defects, congenital abnormalities, or maternal and/or newborn complications.

If required by local regulations, the female participant will be requested to sign a separate pregnancy ICF. Full details will be recorded on a paper Pregnancy Report Form and submitted via email or fax (see the [Safety Mailbox/Fax](#) details on the title page of this protocol), and reporting details will be specified in the trial manual. The investigator will update the Pregnancy Report Form with additional information as soon as the outcome of the pregnancy is known.

If the outcome of the pregnancy is an SAE, then this must be additionally reported as an SAE on the appropriate SAE Report Form.

7.2.1.5.2. Pregnancies in Female Partners of Male Patients

Male patients will be instructed through the ICF to immediately inform the investigator if their partner becomes pregnant during the trial or up to 90 days after they received the last infusion of efgartigimod. A Pregnancy Report Form should be completed by the investigator within 24 hours after learning of the pregnancy and submitted via email or fax (see the [Safety Mailbox/Fax](#) details on the title page of this protocol). Attempts should be made to collect and report details of the course and outcome of any pregnancy in the partner of a male patient exposed to efgartigimod.

The pregnant partner will need to sign an ICF to allow for follow-up on her pregnancy. Once the ICF has been signed, the investigator will update the Pregnancy Report Form with additional information on the course and outcome of the pregnancy. An investigator who is contacted by the male patient or his pregnant partner may provide information on the risks of the pregnancy and the possible effects on the fetus, to support an informed decision in cooperation with the treating physician and/or obstetrician.

7.2.2. Clinical Laboratory Evaluations

In Part A, blood and urine samples for determination of clinical chemistry, hematology and urinalysis will be analyzed at a central laboratory. PD and ADA will be analyzed at a specialty laboratory as indicated in the General Schedule of Assessments for Part A ([Table 1](#)) and [Appendix 3](#). Patients need to be fasting for at least 8 hours prior to the sampling for clinical laboratory tests as from SEB up to EoA.

In Part B, blood and urine samples for determination of clinical chemistry, hematology and urinalysis will be analyzed at local laboratories and results will not be recorded in the eCRF. Blood samples for ADA will be analyzed at a specialty laboratory as indicated in the General Schedule of Assessments for Part B ([Table 2](#)) and [Appendix 3](#).

Additional safety samples may be collected if clinically indicated at the discretion of the investigator.

For all patients of childbearing potential, a urine pregnancy test will be conducted and analyzed locally at the site (on the urine samples taken for urinalysis, if applicable) at all visits in Part A ([Table 1](#)) and at visit 1 and 4 of each Treatment Period, at ITPE visits, at EoS/ED and at the discretion of the investigator in Part B ([Table 2](#)).

The estimated total maximum blood volume needed for a patient during Part A of the trial (when completing the trial up until the last visit) is between 170 mL for a patient who receives 1 Treatment Period only and 362 mL for a patient who receives a maximum of 6 Treatment Periods. The estimated total maximum blood volume needed for a patient during Part B of the trial (when completing the trial up until the last visit) is between 24 mL for a patient who receives 1 Treatment Period only and 100 mL for a patient who receives 6 Treatment Periods.

Clinical laboratory tests will be reviewed for results of potential clinical significance at all time points throughout the trial. The investigator will evaluate any change in laboratory values. If the investigator determines a laboratory abnormality to be clinically significant, it will be considered as a laboratory AE; however, if the abnormal laboratory value is consistent with a current diagnosis, it may be documented accordingly without being reported as an AE.

The details of sampling, handling, storage, and transportation of the samples will be described in the laboratory manual. The actual sample collection date and time must be entered in the patient's source documents and on the central lab assessment eCRF page.

Refer to [Appendix 4](#) for the addresses of the laboratories used for sample analyses and storage.

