
Criteria for Evaluation:
 
Primary Endpoint:
 
 • Incidence and severity of AEs, SAEs, vital signs, electrocardiogram (ECG) and laboratory assessments over the duration of the trial in AChR-Ab seropositive patients. 
Secondary Endpoint:
 
 • Incidence and severity of AEs, SAEs, vital signs, ECG and laboratory assessments over the duration of the trial in the overall population (AChR-Ab seropositive patients and AChR-Ab seronegative patients). 
Tertiary Endpoints:
 
Part A only:
 
 • Total MG-ADL score changes compared to the treatment period baseline of the first cycle (TP_{1B}) and the corresponding TP_{nB} in AChR-Ab seropositive patients. • Total MG-ADL score changes compared to TP_{1B} and the corresponding TP_{nB} in the overall population (AChR-Ab seropositive and AChR-Ab seronegative patients). • Total QMG score changes compared to TP_{1B} and the corresponding TP_{nB} in AChR-Ab seropositive patients. • Total QMG score changes compared to TP_{1B} and the corresponding TP_{nB} in the overall population (AChR-Ab seropositive and AChR-Ab seronegative patients). 	

- Percentage decrease (compared to TP₁B and the corresponding TP_nB) of total IgG level and IgG subtypes in efgartigimod (re-)treated patients.
- Percentage decrease (compared to TP₁B and the corresponding TP_nB) of autoantibodies (anti-AChR antibodies and anti-MuSK antibodies) in efgartigimod (re-)treated patients.

Part A and B:

- Incidence and prevalence of anti-drug antibodies (ADA) to efgartigimod.

Statistical Methods and Plan:

A Statistical Analysis Plan detailing all statistical methods and analyses will be issued before any database lock. A summary of the plan is described below.

All endpoints will be summarized in all enrolled patients by means of descriptive statistics.

Summary statistics will be provided for the continuous endpoints (eg, total MG-ADL score, total QMG score, levels of total IgG and subtypes, anti-AChR/anti-MuSK antibodies, laboratory values, vital signs, ECG) in terms of absolute values, changes from TP₁B or changes from TP_nB, by cycle and available time points.

Frequency tables will be made for all binary variables, ie, AEs and ADA by cycle and overall.

Table 1 General Schedule of Assessments for Part A

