3. TRIAL ENDPOINTS

3.1. Primary Endpoint

Incidence and severity of AEs, serious adverse events (SAEs), vital signs, ECG and laboratory assessments over the duration of the trial in AChR-Ab seropositive patients.

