3.2. Secondary Endpoint

Incidence and severity of AEs, SAEs, vital signs, ECG and laboratory assessments over the duration of the trial in the overall population (AChR-Ab seropositive patients and AChR-Ab seronegative patients).

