5.2.2. Treatment Period Part B

A Treatment Period will include assessments in 4 weekly visits including treatment with efgartigimod in eligible patients in need for (re-)treatment. A new Treatment Period can only be started if it can be completed within the trial duration (up to maximum 3 years or until efgartigimod becomes commercially available or another option to access efgartigimod is available, whichever option comes first).

The following assessments will be performed from visit 1 to visit 4 of each Treatment Period:

- Assessments of disease severity (MG-ADL scale)*
- Weight will be measured at visit 1 and when there is an obvious weight change compared to the last weight assessment*
- Vital signs*
- ECG, only at visit 1 and visit 4 of each Treatment Period*
- Clinical laboratory tests (local labs), only at visit 1 and visit 4 of each Treatment Period.*
- Urinalysis, only at visit 1 and visit 4 of each Treatment Period*
- Urine pregnancy test (only for women of childbearing potential, see [DEFINITION OF TERMS](#)), only at visit 1 and visit 4 of each Treatment Period*
- ADA, only at visit 1 of each Treatment Period*
- Administration of efgartigimod as an IV infusion over a period of 1 hour. Patients will remain at the site for at least 1 hour following the end of the infusion for safety monitoring, based on the patient's clinical status
- Review of concomitant medication

- Assess AEs if any

*These assessments should be performed prior to administration of efgartigimod (predose).

At visit 1 of each Treatment Period, the conditions for (re-)treatment will be checked before administration of efgartigimod (see Section 4.1).

Patients may not receive (re-)treatment with efgartigimod if, at the time of (re-)treatment, they have clinical evidence of bacterial, viral or fungal disease, or any other significant disease which could confound the results of the trial or put patients at undue risk.

If a patient becomes eligible for (re-)treatment with efgartigimod but cannot complete the entire Treatment Period within duration of the trial, the patient should continue to the EoS visit.

If the investigator considers that the patient will not have a clinical benefit from re-treatment then the patient cannot start a new Treatment Period. The patient should then continue to the EoS visit.

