5.4. End of Part A, End of Study, and Early Discontinuation Visit

In case of early discontinuation, the same assessments as scheduled for EoA (day 365) or EoS (day 1095 or when efgartigimod becomes commercially available or another option to access efgartigimod is available, whichever option comes first) must be performed as follows:

For EoA/ED (Part A):

- Assessments of disease severity – the MG-ADL scale should be administered before the QMG scale and before any other assessments except for weight
- Suicidality assessment
- Physical examination
- Weight
- Vital signs
- ECG
- Clinical laboratory tests – Patients should have fasted at least 8 hours before sampling
- Urinalysis
- Urine pregnancy test (only for women of childbearing potential, see [DEFINITION OF TERMS](#))
- Pharmacodynamic biomarkers (anti-AChR antibodies in AChR-Ab seropositive patients only, total IgG and subtypes [IgG1, IgG2, IgG3, and IgG4], and anti-MuSK antibodies in MuSK-Ab seropositive patients only)

- ADA
- Review of concomitant medication and rescue therapy
- Assess AEs if any

For EoS/ED (Part B):

- Before enrolling in ARGX-113-2002 from Part B, patients must first complete the early discontinuation (ED) visit assessments specified in [Table 2](#). The previous efgartigimod IV dose must have been received at least 30 days before entry into ARGX-113-2002. Patients who enroll in ARGX-113-2002 will not return to ARGX-113-1705
- Assessments of disease severity (MG-ADL scale) should be administered before any other assessments except weight
- Physical examination
- Weight
- Vital signs
- ECG
- Clinical laboratory tests (local labs)
- Urinalysis
- Urine pregnancy test (only for women of childbearing potential, see [DEFINITION OF TERMS](#))
- ADA (only in case of ED)
- Review of concomitant medication
- Assess AEs, if any

5.5. **Unscheduled Visit**

It is at the investigator's discretion or at patient's request to initiate an unscheduled (UNS) visit, if deemed necessary for the patient's safety and well-being. All such visits will be documented in the eCRF with any additional required documentation based on the nature of UNS visit.

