5.2 CLINICAL LABORATORY EVALUATION

5.2.1 Available data

Per protocol, for part A, the following laboratory parameters are expected:

- Biochemistry: Creatinine, creatinine clearance (BSA unadjusted), blood urea nitrogen (BUN), glucose, glycosylated haemoglobin (HbA1c), alanine aminotransferase (ALT), aspartate aminotransferase (AST), total bilirubin, gamma-glutamyl transferase (GGT), C-reactive protein (CRP), alkaline phosphatase (ALP), lactate dehydrogenase (LDH), uric acid, albumin, potassium, sodium, total calcium, lipid panel (total cholesterol, high density lipoprotein (HDL), low density lipoprotein (LDL), and triglycerides), international normalized ratio (INR) and activated partial thromboplastin time (aPTT).

Note: for lipids and glucose, only fasted samples (fasting status Y) will be considered

- Haematology: Haemoglobin, platelet count, white blood cell (WBC) count with WBC differential
- Urinalysis: Colour, clarity/appearance, specific gravity, pH, protein, glucose, ketones, blood, bilirubin, urobilinogen, nitrite, leukocyte esterase, and microscopic examination including red blood cell (RBC) count, WBC, cast crystals, bacteria.

Normal ranges are available as provided by the laboratory.

For part B, laboratory samples are analysed locally. Results are not entered in the clinical database, but in case of a clinically significant abnormal result, it is reported as an adverse event.

	
Statistical Analysis Plan
	

ARGX-113-1705
	
Final Analysis
	
Final 1.0 of 20SEP2022

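### Chemistry, haematology and urinalysis values are available for Part A only, and the laboratory tables should say so; separately, haemoglobin has no toxicity-grading row

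*Protocol*

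**What the plan says.** **Endpoints.** The primary endpoint (Protocol 3.1) is the incidence and severity of AEs, SAEs, "vital signs, ECG and laboratory assessments over the duration of the trial in AChR-Ab seropositive patients". The secondary endpoint (3.2) repeats this with "vital signs, ECG and laboratory assessments over the duration of the trial in the overall population". Neither limits the laboratory component to Part A. Protocol 3.3, by contrast, puts the MG-ADL, QMG and pharmacodynamic endpoints under a heading that restricts them to Part A.

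**Part B samples.** Protocol 5.2.2 schedules "Clinical laboratory tests (local labs), only at visit 1 and visit 4 of each Treatment Period", and 5.4 adds a set at the end-of-study or early-discontinuation visit. Protocol 7.2.2 says these samples "will be analyzed at local laboratories and results will not be recorded in the eCRF".

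**What the SAP does with them.** SAP 5.2.1 lists the laboratory parameters as expected for Part A and says of Part B: "Results are not entered in the clinical database, but in case of a clinically significant abnormal result, it is reported as an adverse event". SAP 2.4.3 allocates Part B data to cycles in the same way as Part A data, without separate tables. SAP 2.2.5 derives the worst-case visit from every non-missing post-baseline value. SAP 5.2.3 and the titles of Tables 14.3.2.1 to 14.3.2.3 state no Part A limit.

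**Grading.** SAP 5.2.2 computes toxicity grades only for parameters in Appendix 9. Haemoglobin is on the panel in Protocol Appendix 3 and SAP 5.2.1, and the SAP's definition of a treatment-emergent toxicity uses a haemoglobin grade as its example. Appendix 9.1, as it reads in the text converted from PDF, has no haemoglobin row.

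**The concern.** AEs, vital signs and ECGs continue in Part B and are pooled into the same cycles. A reader who starts from the endpoint wording would take the laboratory tables to cover the same span. A worst-case ECG column draws on both parts. A worst-case laboratory column can draw only on Part A, under the same label. Within a cycle that contains Part B time, the laboratory n falls while the AE rows of that cycle include Part B.

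At stake is the scope of a value-based laboratory safety statement on the primary endpoint. Such statements are in use: Protocol 1.4 already cites the most frequent grade 3 or higher laboratory abnormality in the extension trial.

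The haemoglobin point is separate. If the plan is followed as it reads, Table 14.3.2.3 reports no haemoglobin grades.

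**Working it through.** **1. Which values exist.** The documents give no sample size or event count that bears on this, so the first step is to compare the two parts.

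| | Part A | Part B |
|---|---|---|
| Chemistry, haematology, urinalysis | Central laboratory, values available | Local laboratory, values not in the database |
| Clinically significant abnormality | AE, plus the recorded value | AE only |
| Anti-drug antibodies | Specialty laboratory | Specialty laboratory |
| Urine pregnancy test | Recorded | Recorded |
| Vital signs, ECG | Scheduled and analysed | Scheduled and analysed |

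Sources: Protocol 5.2 to 5.4, 7.2.1.5.1 and 7.2.2; SAP 5.2 to 5.4. The gap concerns the first row only.

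**2. How far the AE route reaches.** Part B AEs are graded with CTCAE v5.0 (Protocol 7.2.1) and tabulated by cycle and overall (SAP 5.1.3). The route depends on the investigator's judgement and yields no values or shifts. Protocol 7.2.2 also allows that "if the abnormal laboratory value is consistent with a current diagnosis, it may be documented accordingly without being reported as an AE". This holds in both parts, but only in Part B is there no database value behind it.

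**3. Effect on percentages.** SAP 5.2.3 counts only patients with data for the parameter, so Part B patients without values do not dilute a percentage. The number of non-missing values is shown in the descriptive statistics (SAP 2.4.1).

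**4. Calendar time.** Inputs: end of Part A at day 365 ±7 and end of study at day 1095 ±7 (Protocol section 5).
- Patient leaving at the end of Part A: 0%.
- Nominal maximum: (1095 − 365)/1095 = 730/1095 = 66.7%.
- With windows: (1088 − 372)/1088 = 716/1088 = 65.8%, to (1102 − 358)/1102 = 744/1102 = 67.5%.

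Actual Part B durations are not given.

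**5. Scheduled Part B draws without recorded values.** With k Part B treatment periods the count is 2k + 1: visits 1 and 4 of each period, plus the final visit. Protocol 5.3 schedules no laboratory tests at Part B intertreatment visits.
- k = 0: 1.
- k = 1: 3.
- k = 6: 13. Six is the number in the protocol's blood-volume example, not a maximum.
- For k of 1 or more, subtract 1 if the first Part B treatment visit is also the end-of-Part-A visit, because those assessments are not repeated.

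**6. Grading rows.** Protocol Appendix 3 names 3 haematology tests and 23 under clinical chemistry, so 3 + 23 = 26.
- With a row in SAP Appendix 9.1 (17): platelets, WBC, creatinine, glucose (low only), ALT, AST, bilirubin, GGT, ALP, albumin, potassium, sodium, calcium, cholesterol, triglycerides, INR, aPTT.
- Without a row (26 − 17 = 9): haemoglobin, creatinine clearance, BUN, HbA1c, CRP, LDH, uric acid, HDL, LDL.
- Calcium is counted through the corrected-calcium row. The SAP panel lists total calcium and SAP 5.2.2 gives no correction formula. If no correction is applied, 10 tests have no row.
- Within the differential, only lymphocytes and neutrophils have rows.
- Six graded analytes are not on the panel: amylase, creatine kinase, lipase, magnesium, CD4 count, fibrinogen.

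**The case against.** The strongest case is that this is a disclosed design choice and only labelling remains.

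- SAP 5.2.1 gives the reason for the smaller n just before the laboratory derivation and presentation rules. This stands: nothing is concealed.
- Other Part A-only tables (QMG, pharmacodynamics, suicidality) carry no Part A label either; the SAP states those limits in its sections on available data. This stands as a description of the SAP's convention. The laboratory case differs because the protocol limits those other items to Part A (3.3 and 7.2.4), whereas it states the laboratory endpoint for the whole trial.
- The endpoint is not empty in Part B, because clinically significant results become graded AEs. This stands. What is missing is the value-based form of the endpoint.
- Rewording a primary endpoint at the final-analysis stage of a descriptive single-arm trial would need a protocol amendment. This stands, and the fix does not require it.
- On haemoglobin, the SAP's example sits in a generic definition, eight other panel tests also lack rows, and the off-panel rows suggest a standard list. All true. The example does not specify what is graded, but it is an outcome that the grading rule, as it reads, cannot produce.

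**Conclusion.** The point holds as a mismatch of scope. Laboratory value summaries, shifts, worst-case results and computed grades support a Part A claim, while the endpoint wording and the tables are not limited to match. The size is between 0% and a nominal 66.7% of a patient's follow-up time without recorded values, depending on the time spent in Part B.

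A reader might infer more than the documents support:
- **That two-thirds of the laboratory data are lost.** The 730 days are calendar time. Part B schedules few draws, so much of that time would have no values even with full recording.
- **That Part B laboratory safety goes unreported.** Clinically significant findings enter the AE tables, and antibody and pregnancy results are still recorded.
- **That the percentages are biased.** They count only patients with data.
- **That haemoglobin goes unanalysed.** It keeps its descriptive statistics and its low/normal/high cross-tabulation, including the worst case. Only value-based grading is missing.

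The haemoglobin conclusion assumes that the row is absent from the SAP as issued. The neighbouring haematology rows are intact in the converted text, which makes a lost row unlikely but does not exclude it.

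**What to change.** **Laboratory scope.** Add one sentence to SAP 5.2.3 and a footnote to Tables 14.3.2.1 to 14.3.2.3, covering the worst-case visit. Both should say that laboratory values, shifts and computed grades cover Part A, up to the end-of-Part-A visit, and that Part B laboratory findings appear in the AE tables. Denominators stay as they are. Align the wording in Protocol 3.1, 3.2 and the synopsis only if the protocol is amended for another reason.

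**Haemoglobin.** Check Appendix 9.1 in the original PDF of the SAP. If the row is absent there too, add it with the limits of CTCAE v5.0, the source the appendix names, so that Table 14.3.2.3 grades haemoglobin. The limits are not in these documents and must be taken from that source.

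**Cost.** A narrower value-based laboratory claim, one sentence, one footnote on three tables, and one grading row with its output. No new data are needed.
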